3.1 Subject Selection

The subjects in this study will be adults with advanced solid tumors refractory to standard therapy or for which no standard therapy exists.

The investigator (physician) or qualified designee will discuss the study with a subject/the legal representative of a subject who is considered a potential candidate for the study. If there is interest in participating in the study, the subject/legal representative will be provided with the informed consent form. The investigator or designee will address any questions and/or concerns that the subject/legal representative may have and, if there is continued interest, will secure written informed consent for participation in the study. Written informed consent and Health Insurance Portability and Accountability Act (HIPAA) authorization (applies to

covered entities in the USA only) will be obtained prior to conducting any protocol-related procedures, including screening evaluations or medication washouts.

3.1.1 Inclusion Criteria

Subjects must meet *all* of the following criteria:

- 1) Men or women at least 18 years of age or older at time of study entry
- 2) Written informed consent and HIPAA authorization (applies to covered entities in the US only) obtained from the subject/legal representative prior to performing any protocol-related procedures, including screening evaluations
- 3) Histologically confirmed advanced solid tumor for which no curative or standard therapies exist
 - a) Twenty subjects will be treated in the dose-expansion phase. Subjects must have measurable disease (as defined in Section 3.7.4) and a histologically confirmed diagnosis of advanced urothelial carcinoma (ie, pure or mixed histology transitional cell carcinoma of the upper or lower urinary tract).
- 4) Karnofsky performance status ≥ 60
- 5) Life expectancy of ≥ 12 weeks
- 6) Prior radiation therapy is allowed provided exposure does not exceed an area of 25% of marrow space.
- 7) Toxicities from previous cancer therapies must have recovered to Grade < 2 .
- 8) Adequate hematological function defined as:
 - Hemoglobin ≥ 10 g/dL
 - Absolute neutrophil count $\geq 1500/\text{mm}^3$
 - Platelet count $\geq 100,000/\text{mm}^3$
- 9) Adequate organ function defined as follows:
 - AST and ALT $\leq 2 \times$ institutional upper limit of normal (ULN)
 - Bilirubin $\leq 1.5 \times$ ULN except in the case of subjects with documented or suspected Gilbert's disease $\leq 5 \times$ ULN
 - Creatinine clearance ≥ 60 mL/min as determined by the Cockcroft-Gault equation (Cockcroft and Gault, 1976) or by 24-hour urine collection for determination of creatinine clearance (creatinine clearance ≥ 50 mL/min will be acceptable for subjects in the dose-expansion phase of the study).

- 10) Women of non-child-bearing potential (defined as being >1 year post-menopausal or surgically sterile) or using effective contraception, eg, use of oral contraceptives with an additional barrier method (since the investigational product may impair the effectiveness of oral contraceptives), double barrier methods (diaphragm with spermicidal gel or condoms with contraceptive foam), Depo-Provera, partner vasectomy, or total abstinence, from the time the informed consent is signed through 30 days after the last dose of MEDI-573. Male subjects with partners of child-bearing potential must be surgically sterile or use contraceptive method as described above from the time of the initiation of MEDI-573 through 30 days after the last dose of MEDI-573.
- 11) Subjects in the dose-expansion cohorts must have at least one lesion that is measurable using RECIST. Other non-measurable lesions are allowed.

3.1.2 Exclusion Criteria

Subjects must have *none* of the following:

- 1) Any concurrent chemotherapy, radiotherapy, immunotherapy, biologic or hormonal therapy for treatment of cancer
- 2) History of allergy or reaction to any component of the MEDI-573 formulation
- 3) Receipt of any chemotherapy or small molecule targeted therapy (such as sorafenib or other tyrosine kinase inhibitors) regimens within 4 weeks prior to the first dose of MEDI-573
- 4) Receipt of any biological or immunological based therapies (including, but not limited to, monoclonal antibody therapy such as bevacizumab or cancer vaccine therapies) within 6 weeks prior to the first dose of MEDI-573
- 5) Receipt of any investigational anticancer therapy within 4 weeks prior to the first dose of MEDI-573, or in the case of monoclonal antibodies, 6 weeks prior to the first dose of MEDI-573
- 6) Previous therapy with monoclonal antibodies directed against IGF-1R
- 7) Poorly controlled diabetes mellitus as defined by the investigator's assessment and/or glycosylated hemoglobin (HbA1c) reading > 8% within 28 days prior to the first dose of MEDI-573
- 8) New York Heart Association Grade ≥ 2 congestive heart failure
- 9) History of myocardial infarction, unstable angina, transient ischemic attack or stroke within the previous 6 months prior to the first dose of MEDI-573
- 10) History of other invasive malignancy within 5 years except for cervical carcinoma in situ (CIS), non-melanomatous carcinoma of the skin or ductal carcinoma in situ (DCIS) of the breast that have been surgically cured

- 11) Evidence of significant active infection requiring antimicrobial, antifungal, antiparasitic, or antiviral therapy or for which other supportive care is given
- 12) Use of immunosuppressive medication other than steroids within 7 days before the first dose of MEDI-573
- 13) Use of systemic steroids within 7 days before the first dose of MEDI-573 (inhaled and topical corticosteroids are permitted). Subjects may take replacement doses of steroids (defined as ≤ 30 mg/day hydrocortisone or the equivalent) if on a stable dose for at least 2 weeks prior to the first dose of MEDI-573.
- 14) Documented brain metastasis
- 15) Pregnancy or lactation
- 16) Previous medical history, or evidence, of an intercurrent illness that in the view of the principal investigator may compromise the safety of the subject in the study
- 17) Clinically significant abnormality on ECG
- 18) Any physical, social or psychiatric condition that would prevent effective cooperation or participation in the study
- 19) Refusal to undergo biopsy of bladder cancer or bladder cancer metastasis pre- and post-administration of MEDI-573 (dose-expansion subjects only)

3.2 Enrollment into the Study

A subject is considered enrolled into the study once written informed consent is obtained. Once informed consent is obtained, a subject identification number (SID) will be assigned by the Sponsor and the screening evaluations may begin. This number will be used to identify the subject during the screening process and throughout study participation, if applicable.

Subjects for whom written informed consent has been obtained will be screened by investigators to assess eligibility for entry into the study. A record of all consented subjects, including screening failures (ie, subjects who are consented but not entered) and the reason for screening failure will be collected in the database.

Subjects who fail to meet all eligibility criteria, who decline further participation, or who are lost to follow-up will not proceed to entry.

Notification of planned dosing should be remitted to the Sponsor within 48 hours of the first dosing.

3.3 Assignment of Treatment Group (Study Entry)

The procedure for study entry is as follows:

- The investigator or designee confirms that written informed consent and HIPAA authorization has been obtained and that the subject meets all eligibility criteria.
- The investigator or designee faxes the eligibility form to the Sponsor with the SID previously assigned by the Sponsor, and the subject's baseline characteristic(s) used to verify that it is the same subject.
- The Sponsor assigns the subject to a cohort.
- A confirmatory fax/email with this information is sent to the investigator/designee.

A subject is considered entered into the study at the time of investigational product administration (Cycle 1, Day 1). Enrollment in the dose-expansion phase can occur simultaneously with Cohorts 6 and 7.

3.4 Blinding

This study is not blinded because only one treatment is used in this study.

3.5 Investigational Product (MEDI-573)

3.5.1 MEDI-573 Supplies and Accountability

MEDI-573 is manufactured by MedImmune, LLC, [name]. MEDI-573 will be distributed to clinical sites using designated distribution centers. MEDI-573 is supplied as a white to off-white, lyophilized powder. Each vial contains [REDACTED] nominal [REDACTED] of active investigational product. MEDI-573 will be reconstituted with 4.0 mL water for injection (WFI) [REDACTED]. The reconstituted solution [REDACTED] will be further diluted into a saline bag for IV infusion.

The MEDI-573 formulation is described in [Table 3.5.1-1](#). MEDI-573 must be stored at 2°C to 8°C (36°F to 46°F).

Table 3.5.1-1 MEDI-573 Formulation

Ingredient	[REDACTED]
Active Ingredients: MEDI-573 ^a	[REDACTED]
Inactive Ingredients: Polysorbate-80 Trehalose Dihydrate L-Histidine L-Histidine Hydrochloride Monohydrate	[REDACTED] [REDACTED] [REDACTED] [REDACTED]
Vial Size	[REDACTED]

^a Lyophilized MEDI-573 powder is to be initially reconstituted with 4 mL of water for injection [REDACTED] prior to dilution for intravenous infusion.

The Sponsor will provide the investigator with adequate quantities of MEDI-573. The investigator is required to maintain accurate Investigational Product (IP) accountability records of use of the MEDI-573 vials. The investigator-appointed IP Manager/site pharmacist will be responsible for IP accountability and dose preparation. Upon completion of the study, copies of all study IP accountability records will be returned to the Sponsor.

Specific details regarding IP supplies, dose preparation, and accountability will be provided in the IP Manual supplied to the sites.

3.5.2 Treatment Regimens

Subjects will be treated in the dose-escalation phase of the study with 1 of 5 dosage levels of MEDI-573 [REDACTED] (Table 3.5.2-1) administered as [REDACTED] IV infusion once every 7 days, on Days 1, 8, and 15 of repeating 21-day cycles (Cohorts 1 through 5). Two additional dose escalation cohorts will evaluate an alternate every-3-week treatment schedule: [REDACTED] Cohort 6 and [REDACTED] Cohort 7, if applicable, administered as [REDACTED] IV infusion on Day 1 of each 21-day cycle. [REDACTED]. The decision to continue enrollment in Cohort 7 [REDACTED] will be based on the Sponsor's assessment of PK, pharmacodynamic, IM, and safety assessments obtained from subjects' exposure to MEDI-573 at the [REDACTED] Cohort 6. The rules for enrolling in the next higher cohort are described in Section 4.9.

The dose-expansion phase will evaluate PK and pharmacodynamic parameters and determine tumor response in approximately 20 subjects with advanced urothelial carcinoma (eg, bladder cancer). Two cohorts of approximately 10 subjects each will be examined in the dose-expansion phase at dose levels [REDACTED] every 7 days. The first 10 subjects enrolled into the dose expansion phase will receive doses of MEDI-573 [REDACTED] every 7 days. The decision to continue enrollment of subjects in the lower [REDACTED] dose-expansion cohort will be based on pharmacodynamic assessments of tissue obtained from subjects pre and post exposure to MEDI-573 at the [REDACTED] dose level. In the event there is insufficient activity at the tissue level in the higher dose expansion cohort, the sponsor may halt dose expansion and no additional subjects will be enrolled into the expansion phase.

In the dose escalation phase (Cohorts 1 through 5 only) and the dose expansion phase, in Cycle 2 and beyond, a dose can be delayed up to 7 days based on hematologic and nonhematologic toxicities, according to the conditions described in Section 3.5.5, but all 3 doses (Cohorts 1 through 5 and the dose expansion phase) must be completed within the cycle in order for the cycle to be considered complete. Subjects who do not receive all required doses within a cycle will not advance to the next cycle and will be removed from treatment. Each new cycle will begin 7 days after the last dose of the previous cycle (Cohorts 1 through 5 and the dose expansion phase). Subjects in Cohorts 6 and 7 cannot have a delay in treatment due to hematologic or nonhematologic toxicities. For Cohorts 1 through 5 and the expansion phase, all visits during Cycle 2 and subsequent visits may occur in a ± 2 -day window to accommodate schedule changes, but doses of MEDI-573 must not occur more frequently than every 6 days. For Cohorts 6 and 7 (if applicable), all visits during Cycle 2 and subsequent visits may occur in a + 2-day window to accommodate schedule changes, but dosing of MEDI-573 must not occur more frequently than every 21 days.

Treatment with MEDI-573 will continue until unacceptable toxicity, documentation of disease progression, or other reasons for subject withdrawal. Rules for dose-escalation are described in Section 4.9. Intra-subject dose-escalation will not be allowed. Dose reduction for toxicities other than DLTs will be allowed as described in Section 3.5.5.

Table 3.5.2-1 Summary of Dose Cohorts

Dose Cohort	Number of Subjects	MEDI-573 Dose
1	3-6	[REDACTED] IV infusion once every 7 days
2	3-6	[REDACTED] infusion once every 7 days

Table 3.5.2-1 Summary of Dose Cohorts

Dose Cohort	Number of Subjects	MEDI-573 Dose
3	3-6	██████████ IV infusion once every 7 days
4	3-6	██████████ IV infusion once every 7 days
5	3-6	██████████ IV infusion once every 7 days
6	3-6	██████████ V infusion once every 21 days
7 (if applicable)	3-6	██████████ IV infusion once every 21 days
Dose-expansion	Up to 20	██████████ IV infusion once every 7 days

IV = intravenous

Note: The dose-expansion phase will evaluate PK and pharmacodynamic parameters and determine tumor response in approximately 20 subjects with advanced urothelial carcinoma (eg, bladder cancer).

3.5.3 Investigational Product Preparation

The dose of IP for administration must be prepared by the IP Manager/site pharmacist or designee using aseptic technique. Detailed instructions regarding IP preparation can be found in the IP Manual that will be provided to the IP Manager/site pharmacist.

The volume (dose) of MEDI-573 will be calculated based on the subject's body weight (kg) (obtained prior to the first administration of MEDI-573 in each treatment cycle) and the subjects dose level (mg).

3.5.3.1 Reconstitution of MEDI-573 Vials

Each MEDI-573 vial will be reconstituted with 4.0 mL of sterile water for injection (WFI) for each vial. To reconstitute the lyophilized product, slowly add 4.0 mL of sterile WFI to the vial. The vial should be tilted slightly and gently rotated or swirled for 30 seconds or until dissolution is complete. Do not shake or vigorously agitate the vial. This is a critical step to avoid prolonged foaming. Reconstituted MEDI-573 should stand undisturbed at room temperature for a minimum of 2 minutes until the solution clarifies. Reconstituted MEDI-573 does not contain a preservative and should be administered promptly (no longer than 6 hours) after reconstitution. MEDI-573 is used as a single-use vial and any unused portion must be discarded.

3.5.4 Administration of Investigational Product

All subjects must be weighed (according to institutional practice) prior to each treatment cycle for calculation of MEDI-573 dosing.

MEDI-573 will be administered to subjects on an outpatient basis as follows:

- 1) Before the MEDI-573 infusion is started, epinephrine 1:1,000, dexamethasone 10 mg, and diphenhydramine (50 mg), or another functionally equivalent H1 blocker, for IV administration and resuscitation equipment for the emergency management of an anaphylactic reaction will be available.
- 2) MEDI-573 will be administered as a 60-minute IV infusion once every 7 days (Cohorts 1 through 5 and the dose expansion phase) or as a 90-minute IV infusion once every 21 days (Cohorts 6 and 7). The Investigator or his/her qualified designee will infuse MEDI-573 until the entire dose is delivered over the infusion period. Vital signs (temperature, respiration rate, pulse, and blood pressure) will be measured immediately prior to MEDI-573 infusion, at every 15 minutes (± 5 minutes) during the MEDI-573 infusion, at the completion of the infusion (± 5 minutes) and 30 and 60 minutes (± 5 minutes) after completion of the MEDI-573 infusion and will be captured in the subject's source documents.
- 3) In the event of an infusion-related reaction, the infusion rate of MEDI-573 may be decreased by 50% or interrupted until resolution of the event (up to 4 hours) and re-initiated at 50% of the initial rate until completion of the infusion. Acetaminophen 650 mg and/or an antihistamine (eg, diphenhydramine 50 mg) or equivalent medications per institutional standard may be administered. Alternatively, or in addition, the rate of infusion of MEDI-573 may be diminished at the discretion of the investigator. Any such activities must be recorded appropriately. If the infusion reaction is severe or prolonged, methylprednisolone 100 mg (or the equivalent) should be administered as well. In such subjects who experience an infusion reaction, prophylactic administration of acetaminophen and/or diphenhydramine or the equivalents may be considered for subsequent administration of MEDI-573.
- 4) Subjects will remain at the study site for at least 60 minutes after the MEDI-573 infusion for medical monitoring.

Since the compatibility of MEDI-573 with other IV medications and solutions, other than 0.9% Sodium Chloride for Injection, is not known, the MEDI-573 solution should not be infused through an IV line in which other solutions or medications are being administered. The date, start time, and completion time of MEDI-573 administration must be recorded in source documents.

3.5.5 Dose Modifications of MEDI-573 Due to Toxicity

Dose modifications of MEDI-573 will be based on hematologic and nonhematologic toxicities that cannot be attributed to another cause such as disease progression or accident following the first cycle of treatment ([Table 3.5.5-1](#)). Both hematologic and nonhematologic toxicities will be graded according to NCI CTCAE V3.0. All DLTs must be documented as an AE on the source document.

Table 3.5.5-1 MEDI-573 Dose Modification Table

Hematologic or Nonhematologic Toxicity	Dose Modification of MEDI-573
Grade ≤ 1	None
Grade 2	
Cohorts 1 through 5 and the Expansion Phase
 
Withhold MEDI-573 for up to 7 days until resolution to Grade ≤ 1 or baseline and resume at current dose level. Grade 2 laboratory toxicities that do not have clinical significance may not require dose delay. The Medical Monitor should be consulted in the event of Grade 2 laboratory toxicities that are deemed clinically insignificant to determine if dosing may continue.
 
Discontinue MEDI-573 if MEDI-573 is withheld for > 7 days without resolution of toxicity to Grade ≤ 1 or baseline unless clearly attributable to another cause such as disease progression or accident.
 
Cohorts 6 and 7 (if applicable)
 
The Medical Monitor should be consulted in the event of Grade 2 laboratory toxicities that are deemed clinically insignificant to determine if dosing may continue.
 
Discontinue MEDI-573 if the toxicity does not return to Grade ≤ 1 or baseline prior to Day 1 of the subsequent cycle unless clearly attributable to another cause such as disease progression or accident.

Table 3.5.5-1 MEDI-573 Dose Modification Table

Hematologic or Nonhematologic Toxicity	Dose Modification of MEDI-573
Grade 3 or 4	
First Occurrence:
 
Cohorts 1 through 5 and the Expansion Phase: Withhold MEDI-573 for up to 7 days until resolution to Grade ≤ 1 or baseline. Discontinue MEDI-573 if no clinical benefit has been documented . If MEDI-573 is withheld for > 7 days without resolution of toxicity to Grade ≤ 1 or baseline, discontinue MEDI-573 regardless of clinical benefit
 
Cohorts 6 and 7 (if applicable) Discontinue MEDI-573 if no clinical benefit has been documented and the toxicity does not resolve to Grade ≤1 or baseline by Day 1 of the subsequent cycle.
 
For all subjects who experience a Grade 3 or 4 toxicity that resolves as above, and who have achieved some degree of clinical benefit while on MEDI-573 therapy, the Food and Drug Administration (FDA) will be consulted regarding the possibility of continued administration of MEDI-573. MEDI-573 therapy should not be continued without agreement from the FDA.
 
Second Occurrence: Discontinue MEDI-573.

If Grade ≥ 3 toxicity that is at least possibly attributable to MEDI-573 is observed in a subject in the second or greater cycle, dose escalation will be temporarily suspended to review the cumulative safety data. Such an event may prompt cessation of dose escalation or modification of the dose-escalation scheme, including lowering of subsequent doses from the first cycle dose, if appropriate. Subjects may continue to receive MEDI-573 during this review and subjects may continue to be enrolled into an open cohort until a determination of necessary action, if any, is made.

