4.7 Interruption or Discontinuation of Study Dosing in Individual Subjects

An individual subject will not receive any further investigational product if any of the following occur in the subject in question:

- 1) Withdrawal of consent
- 2) Grade 2 or greater allergic reactions. Grade ≤ 3 infusion reactions that respond to medical therapy or slowing the infusion rate and are of limited duration will not necessitate dose interruption or discontinuation. Any infusion or allergic reaction that necessitates the use of systemic pressor agents will cause dose discontinuation in that subject.
- 3) Pregnancy or intent to become pregnant
- 4) DLT (see Section 4.10 for definition of DLTs, dose escalation phase only).
- 5) Occurrence of Grade 3 or Grade 4 hematologic or non-hematologic toxicity after the first cycle of treatment
- 6) Grade ≥ 2 toxicities (after completion of Cycle 1) that do not return to Grade ≤ 1 or baseline within 7 days unless clearly attributable to other causes such as disease progression or accident.
- 7) Grade ≥ 2 toxicities that cause a cumulative delay of ≥ 21 days in 3 consecutive cycles (Cohorts 1 through 5 and the expansion phase)
- 8) Documentation of disease progression

- 9) Event which in the opinion of the investigator contraindicates further dosing such as intercurrent illnesses, significant drug toxicities or complications if judged by the investigator to be in the best interest of the subject
- 10) Subject non-compliance
- 11) Treatment with another investigational agent
- 12) Initiation of alternative anticancer therapy

Subjects who are permanently discontinued from investigational product will be followed for the full study period (through 30 days after the last dose of MEDI-573), including the collection of any protocol-specified blood and urine specimens, unless consent is withdrawn.

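### Section 4.7 item 5 and Table 3.5.5-1 give different rules for a first Grade 3-4 toxicity after Cycle 1, and the Cohorts 6-7 cell of the table leaves out two stops

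*Protocol*

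**What the plan says.** Protocol 4.7 opens its list with: "An individual subject will not receive any further investigational product if any of the following occur in the subject in question". Item 5 of that list is: "Occurrence of Grade 3 or Grade 4 hematologic or non-hematologic toxicity after the first cycle of treatment". It sets no condition on clinical benefit, resolution, earlier events or FDA agreement. Item 2 separately exempts infusion reactions of Grade 3 or lower that are brief and respond to treatment or a slower infusion. Item 6 stops dosing for Grade 2 or higher "toxicities (after completion of Cycle 1) that do not return to Grade" 1 or below, or baseline, within 7 days. It names no cohorts, whereas item 7 is limited: "days in 3 consecutive cycles (Cohorts 1 through 5 and the expansion phase").

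Protocol 3.5.5, Table 3.5.5-1, also deals with toxicity after the first cycle, where no other cause explains it. Its Grade 3-4 row says, for a first occurrence:

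- **Cohorts 1-5 and expansion:** hold for up to 7 days. Stop if no benefit is documented. Stop if still unresolved after more than 7 days, whatever the benefit.
- **Cohorts 6-7:** "Discontinue MEDI-573 if no clinical benefit has been documented and the toxicity does not resolve to Grade" 1 or below, or baseline, by Day 1 of the next cycle.
- **All subjects whose toxicity resolved and who had some benefit:** "the Food and Drug Administration (FDA) will be consulted regarding the possibility of continued administration of MEDI-573", and "MEDI-573 therapy should not be continued without agreement from the FDA".

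The row ends: "Second Occurrence: Discontinue MEDI-573". The Grade 2 row for Cohorts 6-7 stops dosing if the toxicity has not resolved before Day 1 of the next cycle, with no benefit condition and an exception only for another clear cause. Section 3.5.2 allows Cohorts 6-7 no dose delay for toxicity.

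**The concern.** A stopping rule for an individual subject should give one answer, and here two current sections give different ones. Under item 5 a first Grade 3-4 event after Cycle 1 is the end of treatment, so the hold, the FDA route and the second-occurrence line can never operate. Under the table they can. Neither section refers to the other for an exception, and no precedence is stated. A site may reasonably start from either: the Overview (2.4) sends individual discontinuation to 4.7 but dose reduction to 3.5.5, and 3.5.2 sends toxicity delays to 3.5.5.

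The Cohorts 6-7 cell adds a second problem. By joining its two conditions with *and*, it is looser than the weekly cell for the same grade. For unresolved toxicity it is also looser than the Grade 2 rule for the same cohorts, so the milder toxicity has the firmer stop. These cohorts may not delay for toxicity, so a subject who is not stopped is due the next dose on schedule. The study is the first in humans.

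**Working it through.** No sample size, power or error rate is involved and the plan gives no figure to reproduce. The check sets the rules side by side for a first Grade 3-4 toxicity after Cycle 1, outside the infusion reactions in 4.7 item 2. The two facts that matter are whether benefit is documented and whether the toxicity resolved in time: 2 x 2 = 4 states.

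| State | 4.7 item 5 | Table: Cohorts 1-5 and expansion | Table: Cohorts 6-7 |
|---|---|---|---|
| Benefit, resolved | Stop | FDA route | FDA route |
| Benefit, unresolved | Stop | Stop | No stop ordered |
| No benefit, resolved | Stop | Stop | No stop ordered |
| No benefit, unresolved | Stop | Stop | Stop |
| Mandatory stops | 4 of 4 | 3 of 4 | 1 of 4 |

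1. **Express contradiction.** In the first row the table opens a route to continue where item 5 bars it: 1 of 4 states, in every cohort. Every event that the table covers also falls under item 5, except the item 2 infusion reactions. The table's limit to toxicity without another cause therefore does not remove the conflict.
2. **Missing stops.** The Cohorts 6-7 cell has 3 - 1 = 2 fewer stops than the weekly cell. The FDA paragraph fills neither gap, because it is written for resolved toxicity in benefiting subjects.
3. **Protocol as a whole.** Item 5 stops all four states, and item 6 also catches unresolved toxicity after 7 days. States with no stop in either section: 0 of 4.
4. **Resolution limit.** Item 6 says 7 days for everyone; the Cohorts 6-7 cells run to Day 1 of the next cycle. Item 5 acts at once on Grade 3-4, so on the current text this difference bites mainly for Grade 2. The protocol does not say when the 7 days start, and Cohorts 6-7 have a +2-day visit window, so no day counts are given.
5. **Reach.** The contradiction covers all 21 to 42 evaluable escalation subjects and about 20 expansion subjects. The missing stops concern Cohorts 6 and 7: 2 x 3 = 6 to 2 x 6 = 12 evaluable subjects if both enroll. Only those with such an event after Cycle 1 are affected. The protocol gives no event rate for that period, so no expected count is offered.

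**The case against.** The strongest reply is that 4.7 already stops these subjects, so nobody is left without a rule. That stands. A reader might infer that a Cohorts 6-7 subject with unresolved Grade 3-4 toxicity could be dosed with nothing in the protocol against it. The documents do not support this: items 5 and 6 apply, and item 9 lets the investigator stop. The gap is also narrower than the cell suggests. An event that has improved to Grade 2 by Day 1 could be read under the Grade 2 cell, which orders a stop, and the FDA sentence might be taken as a general brake. Neither reading is stated, and neither reaches the no-benefit, resolved state.

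A reader might also infer that the strict rule is the intended one, because the amendment log (Appendix 4) shows item 5 tightened from recurrence to occurrence in Version 2.0. But the log also shows the table revised later, in Amendment 5, to cover Cohorts 6-7, and the current table still carries the FDA route. Item 5 could equally be the stale text.

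Finally, a reader might treat 4.7 as always the stricter text and simply declare that it prevails. It is not. Item 2 is looser than the table's Grade 3 row for some infusion reactions. For Grade 2 toxicity starting late in a Cohorts 6-7 cycle, the table's limit can fall before item 6's 7 days are up.

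**Conclusion.** The point holds as an inconsistency in current protocol wording that should be fixed. Item 5 and the table expressly conflict in 1 of 4 states in every cohort. The Cohorts 6-7 cell omits 2 of 4 stops that the weekly cell has. In 0 of 4 states is there no stop anywhere in the protocol. The practical risk is a decision made from Table 3.5.5-1 alone, or an FDA consultation about a continuation that 4.7 forbids.

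Determination of the maximum tolerated dose is not affected, because dose-limiting toxicities are assessed in Cycle 1 only. The conclusion rests on the literal current text of both sections and on leaving the item 2 infusion reactions aside. It makes no claim about which rule the sponsor meant.

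**What to change.** (a) Reword the Cohorts 6-7 Grade 3-4 cell with *or*: stop if no benefit is documented; stop also if the toxicity is not back to Grade 1 or below, or baseline, by Day 1 of the next cycle, whatever the benefit.

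(b) Choose one rule for all cohorts. Either add to item 5 an exception for continuation agreed with the FDA under Table 3.5.5-1, keeping (a), or delete the table's hold, FDA and second-occurrence text so that the Grade 3-4 row simply orders discontinuation, in which case that row replaces (a). In both cases carry the item 2 infusion-reaction exception into item 5 and the table. The choice is clinical and belongs to the sponsor.

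(c) For Cohorts 6-7, make item 6 use the table's limit, Day 1 of the next cycle. No drug is given in between.

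Do not add a blanket statement that 4.7 prevails, for the reason given under the objection. The cost is amendment wording only: no change to sample size, visits or data collection.
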